#### Safety Monitoring of the Vaccine

On each study day (Days 0,7,14 and 21) clinical history and physical examination will be carried out (Appendix IV). The safety and reactogenicity of the vaccine will be monitored in the subjects by observing for 30 minutes after each dose for occurrence of immediate adverse experiences. On 3 consecutive days after each dose parents will be interviewed for 24 hour recall of symptoms by the health workers and the physician by home visits each day. All side-effects will be recorded in reaction surveillance forms for local and systemic reactions (Appendix V). Reported symptoms will be graded as mild, moderate and severe. In case of serious adverse effects the data will be entered in a separate form (Appendix V). The study subject will be hospitalized at the CRSC of ICDDR,B under supervision of the clinician monitoring the safety of the vaccine. Sample collection

Stool: Stool will be collected prior to vaccination (3 days prior to initial immunization) and subsequently at follow-up visits 7 days after intake of the first as well as 7 days after intake of the second dose of the vaccine. Routine examination of stools will be carried out to detect parasites. Bacteriological examination will be carried out to exclude the presence of enteric pathogens (WHO, 1987). Five lactose-fermenting colonies will be tested for colonization factor expression by dot blot immunoassay techniques and for the enterotoxins LT and ST. Stools will be also be tested prior to intake of the second dose and tested similarly. The stools will also be tested to exclude the presence of ETEC by assaying for LT and ST using the GM1-ELISA technique ([name] and Holmgren, 1978; [name] et al., 1986). Stools will also be collected for preparing faecal extracts for antibody and cytokine assays. Faecal extracts will be prepared (Qadri et al., 1997) and stored at -70°C until tested.

**Blood**: Venous blood will be collected from the vaccinees prior to immunization and 7 days after intake of each dose of the vaccine. About 3 ml blood will be collected from vaccinees in the age group ranging from 2-3 years of age, in younger children (<18 months) 1.5 ml of blood samples will be collected. For the children in the 6 months to 18 months of age since the volume of blood will be less, these will only be used only for antibody assays. Total and differential counts of blood and hematocrit will be carried out in the clinical laboratory of ICDDR,B. Cytokine responses will be studied in the serum and in the feces. In older children, ASC responses and cytokine assays with stimulation with CF antigens will be carried out.

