## **Ethical Assurance for Protection of Human Rights**

Describe in the space provided the justifications for conducting this research in human subjects. If the study needs observations on sick individuals, provide sufficient reasons for using them. Indicate how subject's rights are protected and if there is any benefit or risk to each subject of the study.

Signed consent will be obtained from parents for participation of the children in the study for vaccination and specimen collection (Appendix I and II). All data related to side-effects of each dose of the vaccine will be examined by a safety monitoring committee. The reaction surveillance will be carried out for 3 days after each dose of the vaccine and recorded systematically (Appendix-IV).

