#### Appendix V

# Adverse event form Surveillance after Primary vaccination Day 1

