1.0 Completeness of dosing. Amount ingested: 1=100% 2=290% 3=<90%

#### 2.0 LOCAL REACTION

| Parameters               |                                   |
|--------------------------|-----------------------------------|
| Abdominal pain           | 1= No 2=Mild 3= moderate 4=severe |
| Cramp                    | 1= No 2= Yes                      |
| Distension               | 1=No 2= moderate 3= severe        |
| Vomiting                 | 1=No 2= Yes                       |
|                          |                                   |
| If yes, number/day       |                                   |
| Other symptoms           | 1=No 2= Yes                       |
| *Diarrhoea [watery stool |                                   |
| or loose stool ]         |                                   |
| If yes above number/day  |                                   |
| (>3)                     |                                   |

\*Diarrhoea defined as passing of ≥ 3 loose or liquid stools per day

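### A fixed 24-hour recall at home visits with no set time can leave hours just after dosing, and gaps between visits, outside the reaction data (minor)

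*Protocol*

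**What the plan says.** Under Safety Monitoring of the Vaccine, the study days are 0, 7, 14 and 21. With two doses given two weeks apart, dosing falls on Days 0 and 14. Staff monitor each child first by "observing for 30 minutes after each dose for occurrence of immediate adverse experiences". After that, follow-up is by home visit: "On 3 consecutive days after each dose parents will be interviewed for 24 hour recall of symptoms". No hour is set for the visit. The same section says where findings go: "All side-effects will be recorded in reaction surveillance forms for local and systemic reactions (Appendix V").

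Appendix V opens with "Adverse event form Surveillance after Primary vaccination Day 1" and continues with Days 2 and 3; the set is repeated after the second dose. As shown, no form is labelled for the dosing day, and there is no field for the time of the dose or of the visit. Every form starts with the item "Completeness of dosing. Amount ingested", so that item does not settle whether Day 1 means the dosing day or the day after. Appendix IV records the date of vaccination but not the hour.

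Ethical Assurance for Protection of Human Rights states: "The reaction surveillance will be carried out for 3 days after each dose of the vaccine". It names Appendix IV as the record, where Safety Monitoring names Appendix V.

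Safety evaluation defines the primary endpoint as any diarrhoea, vomiting or abdominal cramps of at least moderate grade. It gives no start or end. Data analysis compares the proportions with a primary outcome after each dose.

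**The concern.** A recall of fixed length at a visit of unfixed time gives a window that moves with the visit. When the first visit comes late, the part that drops out is the period immediately after dosing. Staff see only the first 30 minutes of it directly. When later visits are more than 24 hours apart, a stretch between two visits is covered by neither recall.

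Vomiting, diarrhoea and cramps make up the primary safety endpoint. An event in an uncovered stretch may go unreported if the question is put as written. Without clock times, nobody could tell afterwards which children were fully covered. The gap cannot be repaired once the interviews are done, so it is worth closing in advance even though it is small.

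**Working it through.** The plan gives no figure here to reproduce. The inputs from the documents are a 24-hour recall, three daily visits, a 30-minute observation and a three-day surveillance period. Visit times are not given, so everything about them below is an assumption.

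**1. Loss at the start.** If the first visit is *t* hours after the dose, a strict 24-hour recall misses the first max(0, *t* − 24) hours. Taking off the 30 minutes seen by staff leaves max(0, *t* − 24.5).

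| First visit (h after dose) | Missed by recall (h) | Of which not directly observed (h) |
|---|---|---|
| 20 | 0 | 0 |
| 24 | 0 | 0 |
| 26 | 2 | 1.5 |
| 28 | 4 | 3.5 |
| 32 | 8 | 7.5 |

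**2. Average loss under a symmetric assumption.** Let dose time and next-day visit time be independent and uniform over the same 8-hour day. The delay beyond 24 h, *D*, then has density (8 − |*d*|)/64 on −8 to 8.

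- Share of late first visits: P(*D* > 0) = 1/2.
- Mean loss: ∫₀⁸ *d*(8 − *d*)/64 d*d* = (8³/6)/64 = 8/6 = 1.33 h.
- Share where the recall misses the whole first 30 minutes: P(*D* > 0.5) = (7.5²/2)/64 = 0.44.
- Mean loss beyond the directly observed 30 minutes: (7.5³/6)/64 = 1.10 h.

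**3. How far this depends on the assumption.**

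| Delay beyond 24 h, assumed uniform | Mean loss (h) | Recall misses whole first 30 min |
|---|---|---|
| All visits at or before 24 h | 0 | 0% |
| −2 to +2 h | (2²/2)/4 = 0.5 | 1.5/4 = 37.5% |
| 0 to +8 h (every visit late) | 8/2 = 4 | 7.5/8 = 94% |

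The last row requires that no visit ever comes early. The protocol does not say that, so it is an upper case and not an estimate.

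**4. Gaps between later visits.** If two visits are *g* hours apart, the second recall misses max(0, *g* − 24) hours. If visit times vary independently from day to day as in step 2, each interval loses 1.33 h on average. The three intervals after a dose then lose 3 × 1.33 = 4 h, or 4/72 = 5.6% of three days. If each household is visited at a steady hour, the second and third intervals lose close to nothing.

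**5. Full coverage is possible.** Visits at 24, 48 and 72 h cover dosing to 72 h with no gap. A first visit at 20 h followed by visits 24 h apart also has no gap, but the third recall ends at 20 + 48 = 68 h.

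**The case against.** The strongest reply is that the plan loses nothing by design. A first visit at or before 24 hours covers the whole time since dosing, and no section calls for late visits. The instruction to record all side-effects on Appendix V stands in the same paragraph as the 30-minute observation and naturally includes it. The first form after each dose has items for vomiting, cramp, pain and stool count that can hold such a finding. The endpoint definition sets no window, so it excludes no period. A parent asked about the last day may well mention vomiting from 25 or 26 hours earlier. The exact prompt could also be settled in form-completion instructions, and the endpoint window in an analysis plan.

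Most of this stands, and it rules out several stronger readings that a reader might infer:

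- *The 30-minute findings are lost.* Not supported. There is no labelled box, but they have a stated destination.
- *The dosing day is outside the primary endpoint.* Not supported. This would rest on form labels alone.
- *No timetable covers dosing to 72 hours.* Wrong, as step 5 shows.
- *Visits will be late because only three health workers are budgeted.* Not supported. On the larger reading of the sample size (158 in each age group), 316 × 6 = 1,896 visits fall within the first nine months. At an assumed 21 working days a month, that is 1,896/189 = 10 a day, or three to four per worker.
- *The result leans towards no difference.* Not shown. Missed events would shrink a difference only if an early excess existed in one arm. The documents give no figure on the timing of reactions, and with blinding there is no reason for visit times to differ by arm.

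What remains is that the recall length is not left open. It is written as 24 hours, while the visit time is open. Later instructions would have to depart from that wording to close the gap.

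**Conclusion.** The point holds as a minor one. A strict 24-hour recall at visits of unfixed time leaves the start of the post-dose period uncovered whenever the first visit is more than 24 hours after the dose, and leaves gaps whenever later visits are more than 24 hours apart. Under the symmetric 8-hour-day assumption, about half of first visits are late and the mean loss is about 1.3 h per dose. Other assumptions give 0 to 4 h. All these figures assume that parents answer the question strictly as put, which makes them upper values for what would go unreported under each timing assumption.

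The documents show a possible gap in capture, not an actual exclusion of events. How many events it would affect, and whether it would alter the comparison between arms, cannot be worked out from them. The missing 30-minute box and the differing appendix references are matters of form detail.

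**What to change.** - On the Day 1 form after each dose, ask about symptoms *since the dose*. On the Day 2 and Day 3 forms, ask about symptoms *since the last visit*. Change the recall wording in Safety Monitoring of the Vaccine to match.
- Add fields for the clock time of the dose and of each visit.
- State that findings from the 30-minute observation are entered on the first Appendix V form after that dose.
- Add one sentence to Safety evaluation: the primary endpoint counts any qualifying event from dosing through the Day 3 visit, after each dose.
- Reconcile Ethical Assurance (Appendix IV) with Safety Monitoring (Appendix V) on which form records the reaction surveillance.

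The cost is form wording and one sentence of protocol text. No visit, staff or sample is added. The change has to be made before the first dose, because the missing hours cannot be recovered later.

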#### Mononuclear cells and plasma:

Blood will be centrifuged on Ficoll-paque for separation of plasma and mononuclear cells (MNC) for the ASC assays. Plasma samples will be stored at -70°C for cytokine assays or at -20°C for antibody assay. The MNC will be used for the antibody secreting cell responses.

#### Detection of antibody secreting cells (ASCs)

The Ficoll-separated MNCs will be assayed for total and ETEC -specific numbers of ASC by the two-colour ELISPOT technique (Czerkinsky et al., 1988; Wenneras et al., 1992). Purified vaccine-specific CF-ASC response of the IgA/IgM isotype (CFA/I and, CS1) (Evans et al., 1979, Klemm et al., 1985) and recombinant CTB-ASC response of the IgA/IgM isotype (Sanchez et al., 1989) will be used. A significant response will be determined if the vaccine specific ASC response as  $\geq 2$  fold increase over baseline value of ASC/ $10^7$  MNC in the baseline sample. Only ASC levels  $\geq 10$  ASCs per  $10^7$  MNCs in the post immunization specimen will be considered a responder.

| Principal ! | westigator: Last | , first, | middle |  |  | <del>-</del> |  |  |
|-------------|------------------|----------|--------|--|--|--------------|--|--|
|-------------|------------------|----------|--------|--|--|--------------|--|--|

#### CF- and CTB-specific ELISA

Pre- and post-immunization serum or plasma samples from vaccinees will be tested for the presence of IgM and IgA antibodies specific for vaccine-associated CFA/I and IgG and IgA antibodies to CTB will be carried out using purified antigens and methods described earlier (Ahren et al., 1993). A ≥2-fold increase in end-point titer between pre- and post immunization titer specimens will be used to signify seroconversion. Vaccine-specific IgA antibodies will also be determined in faecal extracts. For this purpose the vaccine specific response will be expressed as the number of units per microgram and will be calculated by dividing the titers (in units per ml) by the total IgA concentration (in µg per ml). A twofold or greater increase in the specific titers between the pre-immune and post-immunization stage samples will be considered a significant response.

#### Stimulation of MNC from peripheral blood and detection of cytokines

Separated MNC ( $1x10^6$  MNC) will be stimulated with purified CFA/I (Wenneras *et al.*, 1994) and the culture supernatant tested for cytokine production. The cytokines that will be studied include both Th1 (IFN-gamma), Th2 types (IL-4, IL-5) as well as the proinflammatory type (TNF- $\alpha$ ) using ELISA and reverse transcriptase-PCR techniques (James, 1993; Klappworth *et al.*, 1995; Jung *et al.*, 1995). These samples will be frozen at -70°C until testing is carried out.

#### **Safety Monitoring Committee**

All subjects participating in the study will be included for post-dosing safety analysis (those that have completed intake of both doses or have only taken one dose). A data safety and monitoring committee will be setup for this project. Dr. [name], Clinical Scientist from Clinical Sciences Division, ICDDR,B will be responsible for safety monitoring of the vaccine and in setting up the committee.

## **Facilities Available**

Describe the availability of physical facilities at the place where the study will be carried out. For clinical and laboratory-based studies, indicate the provision of hospital and other types of patient's care facilities and adequate laboratory support. Point out the laboratory facilities and major equipment that will be required for the study. For field studies, describe the field area including its size, population, and means of communications. (TYPE WITHIN THE PROVIDED SPACE).

Existing field, hospital, laboratory and office facilities are adequate and are outlined:

## Field site for study

The Public Health and Sciences Division of ICDDR,B has the basic information of demography and health indicators of urban slums in Dhaka. This study will be done in a sample of urban slum population which will be found suitable by the epidemiologist in the study.

#### Clinical facilities

Although this is a field based study, any clinical facility needed in the study will be provided by the clinicians in the Clinical Research and Service Centre of the ICDDR,B hospital. As a benefit all children will be given a month's supply of multivitamin supplement at the end of the study.

#### Laboratory facilities

Existing laboratory facilities are adequate. An ELISA Reader is needed which has been budgeted for the study. Replacement of a computer is needed in the laboratory which will be used for data input, hook-up to the ELISA Reader as well as for word processing.

# **Data Analysis**

Describe plans for data analysis. Indicate whether data will be analyzed by the investigators themselves or by other professionals. Specify what statistical softwares packages will be used and if the study is blinded, when the code will be opened. For clinical trials, indicate if interim data analysis will be required to monitor further progress of the study. (TYPE WITHIN THE PROVIDED SPACE).

### Methods to ensure data quality:

To ensure the quality of data, the study site will be visited by the investigators for random checks. In addition a 5% sample of study subjects will be re-interviewed within one day to re-assess the original interview.

#### Data management

To maintain consistency the data forms will be reviewed by the investigators. This will be carried out to ensure the completeness and accuracy of the data. If necessary additional home visits will be made to recheck entries or fill up missing entries. After editing, data will be entered in an appropriate data entry program that will be suitable for the study.

[figure not shown]
#### Data analysis

Baseline characteristics of the vaccine and placebo groups will be examined for group comparability. Any baseline difference will be controlled for during data analysis. The data for the two age groups will be handled together and will also be analyzed separately to evaluate the responses.

The frequency distribution will be examined to assess the distribution of data. If the data is not normally distributed, decisions about data transformation and on appropriateness of statistical tests will be made. The data from the vaccine and placebo group will be compared to compare the safety of the vaccine by assessing the association with adverse events in each group.

The data from the two groups will also be compared for assessing the immunogenicity of the vaccine. This will be done for the ASC, plasma antibody and faecal antibodies using criteria described above for defining a response in the study subjects.

All subjects receiving at least one dose of study agent will be included in the postdosing safety analysis. The profile likelihood method will be used to assess differences in the proportions of primary outcomes in vaccinees versus placebo recipients after each dose (Newcombe, 1998). For individual symptoms, proportions will be compared with Fisher's Exact test. This test will also be used to assess differences in the occurrence of ASC responses and antibody seroconversion between the two groups after each dose. The number of antigen specific ASC after each dose will be compared between treatment groups by the median test. Within the vaccine group, the one sample rank sum Wilcoxon test will be used to assess whether number of ASC and plasma antibody titer fold increases are boosted after each successive dose. All statistical tests will be interpreted in a two-tailed fashion.

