#### d) Research Plan, Research design and Methods Study Design

This vaccine study will be a randomized, double blinded, placebo controlled trial. Children will be stratified by age (in two age bands, 6 months to 18 months, > 18 months to 3 years) before randomization. In each group each subject will be assigned a sequential number at the time of initial dosing, corresponding to sequentially numbered and randomized set of two single-dose vials of study agent. The codes will be broken after all clinical and laboratory evaluation have been completed.

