#### Sample size calculation

Sample size calculation (N) has been carried out using the formula shown below at a power of 80% and significant difference level at 95%. The number to be recruited for the safety studies on the vaccine has been derived using side-effects data obtained in a similar study (Savarino *et al.*, 1999). Here  $p_1 = 1\%$  and  $p_2 = 11\%$ , (ETEC vaccinees =  $p_1$ ,; placebo control =  $p_2$ ,  $d = p_1 - p_2$ ). Therefore:

$$N = \frac{(Z\alpha/2 + Z\beta)^2 (2pq)}{d^2}$$

A sample size of 106 is calculated for each of the age groups (6 months to 18 years, >18 month to 3 years) in the study population. Considering a 20% prevalence of ETEC and taking into consideration a 15% adjustment of dropout, the number is 126. However since the prevalence of diarrhoea in the population in the

Principal Investigator: Last, first, middle children in this age group is about 25% (Baqui et al. 1993), and this is taken into consideration, 158 children will be recruited in each age group. The subset of study subjects to be studied for the immune response studies from the groups above have similarly been obtained by using conservative estimations (data for the response obtained to the CF antigen CS4, to which the frequency of response was the lowest). Here  $p_1 = 40\%$  and  $p_2 = 11\%$ , a sample size of 40 and with adjustment for 15% dropout, the number to be recruited is 46 in each age group for both the study groups.

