#### Baseline data

Baseline data from volunteers will be collected during the week prior to vaccination by home visits (Appendix III). The laboratory specimens will be collected prior to vaccination on the day of immunization. The laboratory assays will include blood for immunological assays and stool for culture and routine examination for ova and parasites and immunogical assays. These data will serve as baseline values for the study subjects.

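### Plasma and faecal antibody are compared between arms only as a yes/no 2-fold rise; a prespecified baseline-adjusted comparison of log titre would use the same samples with more power

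*Protocol*

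**What the plan says.** Under CF- and CTB-specific ELISA, a plasma response is a 2-fold or greater "increase in end-point titer between pre- and post immunization titer specimens will be used to signify seroconversion". Faecal IgA, expressed per microgram of total IgA, is also called a response at a 2-fold rise.

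Under Data analysis, plasma and faecal antibody are compared between arms through these response criteria, and Fisher's exact test is "used to assess differences in the occurrence of ASC responses and antibody seroconversion between the two groups after each dose". The other quantitative tests do not fill the gap. The median test between arms covers antibody-secreting-cell counts only, and the Wilcoxon test on titre fold increases is confined to the vaccine arm.

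The information needed for an adjusted comparison exists. Samples are taken before the first dose, and of these Baseline data says: "These data will serve as baseline values for the study subjects". In the study design, "Children will be stratified by age" in two bands before randomisation. Data analysis also says that baseline differences, if any, will be controlled for, and that the two age groups will be analysed both together and separately. It gives no method for the adjustment and does not mention titre.

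**The concern.** Immunogenicity is the second of the trial's two specific aims, and it is studied in a subset only. Cutting a pre/post titre pair at a 2-fold rise treats a 1.9-fold and a 0.5-fold change as equal, and likewise a 2.1-fold and a 20-fold change. Fisher's test then takes no covariate, so the promised control of baseline differences has no route into the named analysis. At stake is the chance of detecting a real antibody response, above all within one age group, and an estimate of how large that response is.

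**Working it through.** **Inputs.** From Sample size calculation: 40% versus 11% responders, stated n = 40, raised to 46 for 15% dropout, "at a power of 80% and significant difference level at 95"%. From Data analysis: "All statistical tests will be interpreted in a two-tailed fashion". The Protocol gives no SD of log titre and no pre/post correlation (ρ), so both are assumed below.

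**The plan's own figure.** The printed formula, with p = 0.255, q = 0.745 and d = 0.29, gives (1.960 + 0.842)² × 2 × 0.255 × 0.745 / 0.29² = 35.5 per arm. With a continuity correction the two-proportion formula gives 41, within one of the stated 40, and exact Fisher power at 40 per arm is 81.6%. So 40 behaves as a per-arm number. 40 × 1.15 = 46.

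**Which n applies.** The text gives 46 per age group *for both the study groups*, which can be read two ways.
- 46 covers both arms: 23 per arm in each age group. Pooled, 46 per arm, or 46 / 1.15 = 40 after dropout.
- 46 is per arm: 40 to 46 per arm in each age group, 80 to 92 pooled.

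The clarification list says that samples come from roughly one child in three. If 158 per age group means 316 children, the first reading gives 92/316 = 29% and the second 184/316 = 58%. That favours the first but does not settle it, because 158 could itself be read as per arm (184/632 = 29%).

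**Normal-shift model.** Let log fold-rise be normal with equal SD in both arms, with 11% and 40% above the 2-fold cut. The shift is z(0.89) − z(0.60) = 1.2265 − 0.2533 = 0.973 SD of log fold-rise. With unit titre variance, the fold-rise has variance 2(1 − ρ) and the ANCOVA residual 1 − ρ². The ANCOVA effect is therefore 0.973 × √(2/(1 + ρ)). Power is from the noncentral t with noncentrality effect × √(n/2); Fisher power is by exact enumeration.

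| n per arm | Fisher, 2-fold cut | Log change, no covariate | ANCOVA, ρ = 0.3 / 0.5 / 0.7 / 0.9 |
|---|---|---|---|
| 20 | 45.3% | 85.1% | 96.0 / 93.3 / 90.2 / 86.7% |
| 23 | 53.1% | 89.7% | 97.9 / 96.1 / 93.8 / 91.1% |
| 40 | 81.6% | 99.0% | 100 / 99.9 / 99.7 / 99.3% |
| 46 | 86.7% | 99.6% | 100 / 100 / 99.9 / 99.7% |

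**Where the loss arises (ρ = 0.5).** At 23 per arm the total gain is 96.1 − 53.1 = 43.0 points. Dropping the cut gives 89.7 − 53.1 = 36.6 of these and the covariate 6.4. At 40 per arm the total is 99.9 − 81.6 = 18.3 points, of which 17.4 come from the cut and 0.9 from the covariate.

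**All-or-none model.** Suppose only a fraction of vaccinees respond, each shifting by 1.5 to 3 log2 units. With no mean change on placebo, the SD of log2 fold-rise is 1/1.2265 = 0.815. A shift of 1.5 puts 73% of responders above the cut, so the fraction is 0.29/(0.73 − 0.11) = 47%. A shift of 3 puts over 99% above it, so the fraction is 33%. By simulation with ρ of 0.5 or 0.8, ANCOVA has about 66% to 77% at 23 per arm, 88% to 96% at 40 and 93% to 98% at 46. Fisher stays near 53%, 82% and 87%. The covariate's share is relatively larger here (about 1 to 5 points at 40 per arm), but the cut still accounts for more.

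**Where the gain fades.** At 40 per arm, Fisher power against 11% is 91.3%, 96.6% and 99.7% for vaccine responses of 45%, 50% and 60%. At 80 per arm with 40% it is 98.8%.

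**The case against.** The case for leaving the plan alone has substance. The 2-fold rise is the declared response definition, the subset was sized on responder rates, and the test matches that endpoint. At 40 per arm the stated 80% is met. Immunogenicity is not the primary endpoint, and a separate analysis plan could add titre models. All of this stands, and it limits the point to unused efficiency. It does not remove the point: the Protocol fixes its tests by name and tests titre changes only within the vaccine arm.

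Four stronger readings are tempting, and the documents do not support them.
- A reader might infer that baseline titre and age band are ignored. Baseline is the denominator of the fold-rise, baseline differences are to be controlled for, and the age groups are analysed together and separately. What is missing is a prespecified method.
- A reader might blame the loss on the missing covariate. The table shows that most of it comes from the cut.
- A reader might infer bias, because previously exposed children start high and are less likely to double: under equal variances the log rise correlates −√((1 − ρ)/2) with baseline, or −0.5 at ρ = 0.5. This acts alike in both randomised arms. It costs sensitivity but does not distort the comparison.
- A reader might take 53% as the power of the study. It applies to one age group, on one reading of 46, before dropout. On that reading the pooled comparison has 82% to 87%.

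The rates are also a deliberate floor, based on "data for the response obtained to the CF antigen CS4, to which the frequency of response was the lowest". CS4 is not among the antigens named for the plasma ELISA, which are CFA/I and CTB.

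**Conclusion.** The point holds as a matter of efficiency. No between-arm comparison of antibody magnitude is named, and the baseline adjustment as worded is data-dependent and cannot be done within the named test. At the plan's own rates, ANCOVA gains about 38 to 45 points at 23 per arm and 13 to 18 points at 46 to 40 per arm under a normal shift. Under the all-or-none model the gain is roughly 12 to 24 points at 23 per arm and 6 to 14 at 40 to 46. ANCOVA was ahead in every setting with ρ of 0.5 or 0.8. These sizes rest on an assumed titre distribution and correlation and on the lowest-responding antigen. They shrink to almost nothing at 80 or more per arm or at response rates near 60%.

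**What to change.** In Data analysis, add for each plasma antibody, and for faecal specific IgA per microgram of total IgA, a prespecified ANCOVA after each dose: log post-dose value on arm, log baseline value and age band. Report the adjusted geometric mean ratio with its 95% confidence interval. For these outcomes, let this replace the conditional baseline adjustment. Keep the 2-fold responder rates with Fisher's test alongside. State in Sample size calculation whether 46 is per arm or covers both arms.

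The cost is one paragraph of text, with no new children, samples or assays. A rule is needed for titres below the detection limit, and the added result is a mean ratio, which is less familiar to some readers than a responder percentage.
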